Appendix H: Patient Script to Invite Viewing of Tool w/ Results – Either Intervention Arm

Dear [PATIENT NAME],

This is the HOPE-Genomics Team at City of Hope. You may remember speaking with [consenter] about your participation in the HOPE-Genomics study, involving a web-based education tool for patients with genetic testing at City of Hope. Thank you for completing your first two surveys for the study!

At this time, we would like to invite you to log into the tool to view your genetic test results. You may log into the tool by clicking the following link: <https://hopegenomics.coh.org/login>.

Once you have viewed the tool, we will send you a follow-up survey. We have also attached instructions for viewing the tool.

If you have any problems accessing the tool, we can accommodate in-person visits at City of Hope Duarte campus or remote visits using web conferencing (i.e. Zoom). Please call [INSERT CRA'S PHONE NUMBER] or email us at [contact] if you would like to schedule an appointment to speak with study staff.

If you have any additional questions about this research study, please call the Principal Investigator, [name] at [contact] or the Clinical Research Coordinator, [name] at [contact]. You can also reach the Institutional Review Board at City of Hope by calling [contact].

Thank you for all your help with our research at City of Hope, and we look forward to hearing from you!

The HOPE-Genomics Team

[name], [name], [name], [name], and [name]

Division of Clinical Cancer Genomics

Medical Oncology and Therapeutics Research

Department of Population Sciences

City of Hope Comprehensive Cancer Center

[name]

[name]

Appendix I: Baseline Survey Invitation Letter

Dear [PATIENT NAME],

This is the HOPE-Genomics Team at City of Hope. You may remember speaking with [consenter] recently about your participation in the HOPE-Genomics study. Thank you for your willingness to participate in our research study involving new ways to teach patients about cancer and genetics. It was a pleasure speaking with you!

As we discussed, the first step in the study is to complete a survey about yourself, your cancer care, and your understanding of genetics. This survey takes at least 15-30 minutes to complete. Please complete the following survey, using the provided study ID: [INSERT REDCAP STUDY ID].

[For REDCap]. You can access the baseline survey at this link: [LINK]

[PAPER ONLY]. Please complete the attached baseline survey and mail it back to us in the enclosed self-addressed return envelope.

We have attached two documents to this letter: (1) a pamphlet with information about genomic testing, and (2) an information sheet with further details about the HOPE-Genomics study.

Participation in this study will not involve any treatment. The study is confidential and your responses to survey questions will not be passed along to your medical provider or anyone outside of the study team.

If you have any questions about this research study, please call [CONSENDER'S NAME] at [INSERT CONSENDER'S PHONE NUMBER], or the Principal Investigator, [name] at [contact] or the Clinical Research Coordinator, [name] at [contact]. You can also reach the Institutional Review Board at City of Hope by calling [contact].

Thank you so much,

The HOPE-Genomics Team

[name], [name], [name], [name], and [name]

Division of Clinical Cancer Genomics

Medical Oncology and Therapeutics Research

Department of Population Sciences

City of Hope Comprehensive Cancer Center
[name]
[name]

Appendix J: Pre-Test Survey Invitation Letter

Dear [PATIENT NAME],

This is the HOPE-Genomics team at City of Hope. You may remember speaking with [consenter] recently about your participation in the HOPE-Genomics study. Thank you for completing your first survey!

In preparation for your genomic testing, you may have received education materials and/or resources about cancer and genomic testing. The next step in the study is to complete a survey about your knowledge of genetics. The survey should take approximately 10 minutes. Please complete the following survey, using the provided study ID: [INSERT REDCAP STUDY ID].

[For REDCap]. You can access the pre-test survey at this link: [LINK]

[PAPER ONLY]. Please complete the attached survey and mail it back to us in the enclosed self-addressed return envelope.

Participation in this study will not involve any treatment. The study is confidential and your responses to survey questions will not be passed along to your medical provider or anyone outside of the study team.

If you have any questions about this research study, please call [CONSENDER'S NAME] at [INSERT CONSENDER'S PHONE NUMBER], or the Principal Investigator, [name] at [contact] or the Clinical Research Coordinator, [name] at [contact]. You can also reach the Institutional Review Board at City of Hope by calling [contact].

Thank you so much,

The HOPE-Genomics Team

[name], [name], [name], [name], and [name]

Division of Clinical Cancer Genomics

Medical Oncology and Therapeutics Research

Department of Population Sciences

City of Hope Comprehensive Cancer Center

[name]

[name]

Appendix K: Follow-Up Survey Invitation Letter (10 day/3 month/9 month for Intervention Arms)

Dear [PATIENT NAME],

This is the HOPE-Genomics team at City of Hope. You may remember speaking with [consenter] recently about your participation in the HOPE-Genomics study. Thank you for viewing your genomic test results in the HOPE-Genomics tool for patients at City of Hope!

To help us make this tool the best it can be, we would love to hear your thoughts. There will be 3 follow-up surveys, approximately 10 days, 3 months, & 9 months after receiving your genomic test results. This is the [SURVEY NAME]. This survey will ask you about cancer, genetics, and what you understand about your genetic testing results and cancer. The survey may also ask you about your experience viewing your test results in the HOPE-Genomics tool. Some of the questions may look familiar from an earlier survey. We would like you to complete this survey as well.

[For REDCap]. You can access the [SURVEY NAME] online by using this link: [LINK]. Please complete the survey, using the provided study ID: [INSERT STUDY ID].

[PAPER ONLY]. Please complete the attached survey and mail it back to us in the enclosed self-addressed return envelope.

After completing this survey, you will be provided with a [INSERT 5/\$10] gift card as a thank you for your time and feedback.

Participation in this study will not involve any treatment. The study is confidential and your responses to survey questions will not be passed along to your medical provider or anyone outside of the study team.

If you have any questions about this research study, please call [CONSENTER'S NAME] at [INSERT CONSENTER'S PHONE NUMBER], or the Principal Investigator, [name] at [contact] or the Clinical Research Coordinator, [name] at [contact]. You can also reach the Institutional Review Board at City of Hope by calling [contact].

Thank you so much,

The HOPE-Genomics Team

[name], [name], [name], [name], and [name]

Division of Clinical Cancer Genomics

Medical Oncology and Therapeutics Research

Department of Population Sciences

City of Hope Comprehensive Cancer Center

[name]

[name]

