Psychosocial impact of genetic testing and patient uncertainty will be assessed using both the adapted PAGIS Certainty Scale and the FACToR.²³ The FACToR is a 12-item measure developed by CSER1 colleagues at the University of Washington that applies across disease contexts and also includes items related to uncertainty, test-related distress, and positive experiences. Uncertainty about genetic testing results will be assessed using the PAGIS. A 5-item measure by Read and colleagues (Psychological Adaptation to Genetic Information Scale; PAGIS certainty subscale).⁸

Tool usability/usefulness/acceptability will be assessed for patients who view the HOPE-Genomics tool (Arms 2 and 3) approximately 10 days and 3 months after results disclosure. HOPE-Genomics usability/acceptability will be assessed using two instruments. To assess system usability, we will use the System Usability Scale (SUS).⁹ The SUS is a 10-item measure that evaluates a variety of aspects of system usability including the perceived complexity of a system and the need for support and training to facilitate use. We will also use an adapted version of the Electronic Self-Report Assessment-Cancer (ESRA-C).¹³ The ESRA-C is a 6-item measure that assesses participants' opinions about a web-intervention (e.g., easy and enjoyable, acceptability of time required to navigate, overall satisfaction). The ESRA-C is written at a 5th-grade reading level and is highly reliable (Cronbach alpha 0.76).

Motivations for sharing genetic test results will be assessed using a modified 9-item measure adapted from our CSERII study and the Development of the Informing Relatives Inventory (IRI) by de Gues and colleagues.¹⁰ Patients will be asked to rank the importance of various reasons for sharing genetic test results on a 5-point scale, from "Not At All Important" to "Very Important." This measure will only be included in the 3-month follow-up survey and will be included as an exploratory measure.

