Test-related distress: We hypothesize that patients who view HOPE-Genomics will have lower test-related distress than patients in the usual care group: Patients will be assessed at 3 post-disclosure time points (T1-T3) using the PAGIS Certainty Scale and the FACToR. Some patients may have little test-related distress, whereas others may score higher (e.g., if testing reveals cancer or non-cancer related disease risk). Test-related distress is thought to decrease with time from the disclosure visit. We will summarize test-related distress at each time point, as well as change score. We will examine baseline characteristics to evaluate the potential for bias. In addition to complete case analysis, sensitivity analyses (e.g., using weighted methods) may occur to evaluate bias. We will use clustered Wilcoxon test for mean score comparison between groups at each time point. In addition, mean change in score from T1 to T3 will be modeled using GEE model adjusting for patient characteristics. We will use Autoregressive (AR1) and compound symmetry working correlation matrix to account for repeated measurement correlation and within-physician correlation. The significance of the coefficient will be tested to determine difference between two groups.

General genomic knowledge: We hypothesize that patients in the Return of Results plus Pre-test Education (Arm 3) arm will have better general genomic knowledge than the Return of Results only and Usual Care arms (Arms 1/2). To examine this, we will compare the pre/post test scores between the intervention group (Arm 3) and the control groups (Arms 1/2). The pre/post test scores will be calculated by taking the difference in score between pre/post tests and then comparing the mean differences with an independent T-test between control groups (Arms 1/2) versus the exclusive exposure to the HOPE-Genomics tool educational content (Arm 3). We also hypothesize that Arm 3 will have better knowledge of the difference between germline and somatic testing, as measured in the modified Lung-MAP instrument, which has been adapted and implemented in our survey. We will test this difference as above, testing the mean difference in scores of the modified Lung-MAP instrument across Arms 1 and 2 vs Arm 3.

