Appendix L: 10-Day Follow-Up Survey Invitation Letter (10 day/3 month/9 month for Usual Care Arm)

Dear [PATIENT NAME],

This is the HOPE-Genomics Team from City of Hope. We are reaching out to you because you recently received your genomic test results from your healthcare provider at the City of Hope Comprehensive Cancer Center. Thank you very much for expressing interest in providing feedback about your experience through a follow-up survey!

We would love to hear your thoughts on receiving your genomic test results. There will be 3 follow-up surveys, approximately 2 weeks, 3 months, & 9 months after receiving your genomic test results. This is the [SURVEY NAME]. This survey will ask you about cancer, genetics, and what you understand about your genetic testing results and cancer. Some of the questions may look familiar from an earlier survey. We would like you to complete this survey as well.

[For REDCap]. You can access the 10-day follow-up survey by clicking this link. [LINK]. Please complete the survey, using the provided study ID: [INSERT STUDY ID].

[PAPER ONLY]. Please complete the attached survey at your earliest convenience and mail it back to us in the enclosed self-addressed return envelope.

After completing this survey, you will be provided with a [INSERT 5/\$10] gift card as a thank you for your time and feedback.

Participation in this study will not involve any treatment. The study is confidential and your responses to survey questions will not be passed along to your medical provider or anyone outside of the study team.

If you have any questions about this research study, please call [CONSENTER'S NAME] at [INSERT CONSENTER'S PHONE NUMBER], or the Principal Investigator, [name] at [contact] or the Clinical Research Coordinator, [name] at [contact]. You can also reach the Institutional Review Board at City of Hope by calling [contact].

Thank you so much,

The HOPE-Genomics Team

[name], [name], [name], [name], and [name]

Division of Clinical Cancer Genomics

Medical Oncology and Therapeutics Research

Department of Population Sciences

City of Hope Comprehensive Cancer Center
[name]
[name]

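### The follow-up survey invitations give Arms 2/3 a tool-improvement reason to answer that Usual Care does not get: an avoidable between-arm difference in how self-rated distress and certainty are collected

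*Combined protocol and SAP*

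**What the plan says.** Appendix K is the follow-up invitation for the two intervention arms at 10 days, 3 months and 9 months. It opens with "Thank you for viewing your genomic test results in the HOPE-Genomics tool for patients at City of Hope" and gives this reason to take part: "To help us make this tool the best it can be, we would love to hear your thoughts". It adds that the survey may include questions about the tool.

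Appendix L is the Usual Care invitation to the same three surveys. Its request is "We would love to hear your thoughts on receiving your genomic test results".

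Both letters then describe the content in identical words: "This survey will ask you about cancer, genetics, and what you understand about your genetic testing results and cancer". The baseline and pre-test invitations (Appendices I and J) are each a single letter for all arms.

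On tool questions, Section 4.1.2 states: "Tool usability/usefulness/acceptability will be assessed for patients who view the HOPE-Genomics tool (Arms 2 and 3) approximately 10 days and 3 months after results disclosure". Table 1 likewise shows usability at T1 and T2 only. Under Sections 4.5.1 and 4.5.3, Usual Care receives surveys without tool items.

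Section 6.2.3 plans a between-group comparison of PAGIS and FACToR scores at T1 to T3, on this hypothesis: "We hypothesize that patients who view HOPE-Genomics will have lower test-related distress than patients in the usual care group". The tests are a clustered Wilcoxon test at each time point and a GEE model of mean change from T1 to T3. Section 6 does not mention the difference between the letters.

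**The concern.** Patients know whether they were given the tool, and distress and certainty are ratings they give of themselves. In one group, the letter that leads to those ratings thanks the patient for using the study's product and asks for help in improving it. In the other, it asks about receiving results. If that frame moves the ratings at all, it does so in Arms 2/3 only, and the resulting difference would be read as an effect of the tool. Randomisation does not protect against a difference introduced at measurement, and none of the planned covariate adjustments addresses it.

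The frame is also not needed. At 9 months it does not match the survey, because usability is not assessed then. The single letters used for baseline and pre-test show that the study can write a common invitation.

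**Working it through.** **1. The letters side by side.**
- Surveys covered: the same three in K and L.
- Opening: K thanks the patient for viewing results in the tool. L refers to results received from the provider and thanks the patient for interest in giving feedback on the experience.
- Reason to answer: improving the tool (K); thoughts on receiving results (L).
- Content sentence: identical.

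The difference therefore lies in the opening, the stated reason and K's notice of possible tool questions.

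**2. Which outcomes it can reach.**
- *Distress and certainty (FACToR, PAGIS; T1 to T3):* self-rated and formally compared between groups. Exposed at each time point.
- *Informing relatives:* a reported behaviour, analysed as any/none in Section 6.2.3 and counted in the guideline-concordance measure in Section 6.0. Table 1 marks patient surveys but not record abstraction for it, whereas Section 4.6 lists it among abstracted data. Possibly exposed, to the extent that it rests on self-report.
- *Primary recall:* Section 6.2.1 scores it as correct or not. The letter could act only through who responds, or by cueing patients to the tool.
- *Satisfaction and engagement:* collected, but Section 6.2 specifies no between-arm test.

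**3. The plan's own figure.** Section 6.2.1 assumes 39% against 54%, n = 130 and 260, two-sided 5%.
- Pooled rate = (0.39 + 2 × 0.54)/3 = 0.49.
- SE under the null = √[0.49 × 0.51 × (1/130 + 1/260)] = 0.0537.
- SE under the alternative = √[0.39 × 0.61/130 + 0.54 × 0.46/260] = 0.0528.
- Power = Φ[(0.15 − 1.96 × 0.0537)/0.0528] = 80.2%.

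The stated 80% reproduces. The present point does not depend on it; only the group sizes are carried forward.

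**4. Illustration for a self-rated score.** The shift d (in SD units, Arms 2/3 only) is assumed, with no true effect.
- z = d × √(130 × 260/390) = 9.31d.
- Rejection rate = Φ(z − 1.96) + Φ(−z − 1.96).
- d = 0.05: z = 0.47, rate about 7.5%.
- d = 0.10: z = 0.93, rate about 15%.
- d = 0.20: z = 1.86, rate about 46%.

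This is a simple test of means that ignores within-physician clustering. The planned test at each time point is a clustered Wilcoxon test.

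**5. Illustration for a yes/no self-report.** With an assumed base rate of 39% to 50% and the same group sizes, assumed shifts of 2, 5 and 10 percentage points give about 7%, 15-16% and 47%. For example, for 39% against 44%: SE = √[0.39 × 0.61/130 + 0.44 × 0.56/260] = 0.0527, z = 0.05/0.0527 = 0.95, rate about 16%.

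**6. The change model.** Appendix K is used at T1 and at T3. If the shift is d at both, its contribution to the T1-T3 change is d − d = 0. The figures in step 4 therefore do not apply to the GEE comparison of change unless the shift varies over time.

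**The case against.** The case for leaving the letters alone has real force.

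- **The frame is only part of the letter.** Both letters describe the survey content identically, and K says only that tool questions may appear. This stands, and it means that a neutral text already exists.
- **Exposure varies by channel.** The phone/Zoom script (Appendix P) and the text reminder (Appendix R) carry no tool-improvement request. This stands as partial mitigation. Texts are opt-in and supplement other contact.
- **Arms 2/3 know their assignment anyway,** are reminded to use the tool, and answer usability items at two time points. This stands: the letter adds to an asymmetry that editing it will not abolish. That does not justify keeping the avoidable part.
- **Direction is unknown.** A request to improve a tool may draw criticism as easily as goodwill, and the distress scales concern test results, not the tool. This stands in full.
- **The assumed shifts are not evidence.** The same arithmetic could accompany any suspected measurement bias. This also stands; it shows sensitivity only.

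A reader might go further and infer that the letter biases the primary result. The documents do not support that: wishing to help the tool cannot supply a correct somatic result, and nothing in them indicates differential response or cueing. Nor do they support a claim about tests of satisfaction or engagement, since none is specified between arms.

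**Conclusion.** The point holds in limited form. The two letters create an arm-specific measurement condition at all three follow-ups that serves no need of the outcome comparisons. It matters mainly for the exploratory distress and certainty comparisons at each time point, and possibly for informing relatives where that is self-reported. Neither the direction nor the size of any shift can be derived from the documents.

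The range of about 7.5% to 46% rests on assumed shifts of 0.05 to 0.20 SD, on 130 and 260 analysed, and on independent observations. A reader might take the upper figure as the trial's false-positive rate; it is only what a 0.20 SD shift would do if one existed. The change from T1 to T3 is protected if the shift is constant. The case for acting rests on the low cost of removing the difference, not on a demonstrated bias.

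**What to change.** Use one neutral follow-up invitation for all three arms at all three time points, built on the sentence both letters already contain: "This survey will ask you about cancer, genetics, and what you understand about your genetic testing results and cancer". Delete the tool-improvement sentence and the thanks for viewing the tool from Appendix K, and move its notice of tool questions into the survey. In the 10-day and 3-month surveys for Arms 2/3, introduce the usability items after every item compared between arms, if they are not already there; the questionnaires are not in the documents, so their present order cannot be checked. The merged letter must also settle the timing of the first survey, which K gives as 10 days and L as 2 weeks.

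The cost is a template amendment, with no new data or sample size. The one risk is in the changeover. Appendix U addresses participants who had already consented, so the trial is under way. A patient in Arms 2/3 who had the old letter at T1 and a neutral one at T3 would carry any framing shift into the change score (0 − d = −d), where it now cancels if constant. So apply the new letter, in all arms, only to participants not yet sent their 10-day invitation. Keep the old version for the others throughout their follow-up, and record which version each participant received. The difference in framing then remains for those already in follow-up, which should be stated when the distress results are reported.

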Appendix L: 10-Day Follow-Up Survey Invitation Letter (10 day/3 month/9 month for Usual Care Arm)

Dear [PATIENT NAME],

This is the HOPE-Genomics Team from City of Hope. We are reaching out to you because you recently received your genomic test results from your healthcare provider at the City of Hope Comprehensive Cancer Center. Thank you very much for expressing interest in providing feedback about your experience through a follow-up survey!

We would love to hear your thoughts on receiving your genomic test results. There will be 3 follow-up surveys, approximately 2 weeks, 3 months, & 9 months after receiving your genomic test results. This is the [SURVEY NAME]. This survey will ask you about cancer, genetics, and what you understand about your genetic testing results and cancer. Some of the questions may look familiar from an earlier survey. We would like you to complete this survey as well.

[For REDCap]. You can access the 10-day follow-up survey by clicking this link. [LINK]. Please complete the survey, using the provided study ID: [INSERT STUDY ID].

[PAPER ONLY]. Please complete the attached survey at your earliest convenience and mail it back to us in the enclosed self-addressed return envelope.

After completing this survey, you will be provided with a [INSERT 5/\$10] gift card as a thank you for your time and feedback.

Participation in this study will not involve any treatment. The study is confidential and your responses to survey questions will not be passed along to your medical provider or anyone outside of the study team.

If you have any questions about this research study, please call [CONSENTER'S NAME] at [INSERT CONSENTER'S PHONE NUMBER], or the Principal Investigator, [name] at [contact] or the Clinical Research Coordinator, [name] at [contact]. You can also reach the Institutional Review Board at City of Hope by calling [contact].

Thank you so much,

The HOPE-Genomics Team

[name], [name], [name], [name], and [name]

Division of Clinical Cancer Genomics

Medical Oncology and Therapeutics Research

Department of Population Sciences

City of Hope Comprehensive Cancer Center
[name]
[name]

